For each of the outcomes stated above the following target difference is important for the key stakeholder groups consulted (e.g. patients, clinician, and healthcare funder): from 30.43% to 22.65%.

Using a 5% significance level (alpha 0.05), an intracluster correlation coefficient (ICC) of 0.063 (based on data from the ERNIE2 study in the exact same population), and power of 90% (beta 0.1), this would require **55 clusters of 50 patients** in both arms, resulting in **5500 children**. Drop-outs are unlikely to be a large problem since there will be only 1 study visit complemented by the collection of follow-up information. Imputation of missing values for patient-and/or parent/legal guardian-reported outcomes (if there are any) will be considered. Other outcomes will be collected in the patient health record of the physician.

R code:

We used the n4props-function in the R package CRTSize, using the following command:

n4props(0.3043,0.2265,50,0.063, alpha = 0.05, power=0.9, AR=1, two.tailed=TRUE, digits=3)

Considering the pragmatic nature of this trial and in correspondence with the 10% of practices performing nonconsecutive inclusion of patients (high risk of selection bias) during the ERNIE2 trial, we will perform sensitivity analyses only considering physicians who have recruited a minimum of 10 patients per year. Taking into account the required sample size for this analysis of the primary study outcome as part of the sensitivity analysis, these assumptions result in a total sample size of 6111 patients for the primary study outcome.

Secondary outcomes

To demonstrate non-inferiority in the effect of the diagnostic algorithm including the **clinical decision tree**, **POC CRP test and safety netting advice** on the **secondary outcomes**, we use the following assumptions (based on observed proportions in previous trials in children) (11,27):

Secondary outcome		Proportion in intervention group	Proportion in usual care group	Means + pooled standard deviation (SD)	Clinically significant change*
1.	Time to clinical recovery (days)	NA	NA	Mean intervention group: 4.06 Mean usual care group: 4.15 Pooled SD: 3.89	1
2.	Additional investigations at index and/or during follow-up (%)	9.0%	9.8%	NA	3%
3.	Re-consultations during follow-up (%)	33%	34%	NA	4%
4.	Antibiotic prescribing rate during follow up (%)	7%	8%	NA	2%

* based on consensus from a group of clinical researchers with experience in diagnostic and clinical research

NA: not applicable

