Contact Datum Is kleiner dan of gelijk aan 31/10/2022 ARON 2.En de periode dat ze gerekruteerd hebben tijdens de trial (gemakkelijk te vinden in Redcap - bv 1 mei 2021 t/m 30 november 2022). b.Hoeveel kinderen hebben minstens 1 AB voorschrift gekregen						
Medicatie	BCFI boom	ls gelijk aan	Antibacteriële middelen			
Contact	Datum	ls kleiner dan of gelijk aan	31/10/2022			
Patiëntenadministratie	Geboortedatum	ls kleiner dan of gelijk aan	30/11/2020			
Contact	Datum	ls groter dan of gelijk aan	01/05/2021			
Medicatie	Datum	ls groter dan of gelijk aan	01/05/2021			
Patiëntenadministratie	Geboortedatum	ls groter dan of gelijk aan	01/05/2009			
Contact	Auteur	ls gelijk aan				
Contact	Туре	ls gelijk aan	Consultatie			
Medicatie	Datum	ls kleiner dan of gelijk aan	31/10/2022			

Figure 8. Audit questions (after start of the trial) in CareConnect software (Corilus).

Most software packages, e.g., CareConnect², Daktari³, HealthOne⁴, of which the former dominate the market, have a statistics/search module. This allows for easy and uniform access to the required data.

2. Sample size calculation

The original sample size calculation was based on previous data, assuming an overall prescribing rate of 26.5% in those children recruited for our trial.

The overall prevalence was found to be 18% overall in children recruited in the first 4938 patients recruited in the ARON trial.

If we were to assume a reduction of 5.3% (proportionate to our original reduction) between the usual care group and the intervention group, using a 5% significance level (alpha 0.05), an intracluster correlation coefficient (ICC) of 0.063 (based on data from the ERNIE2 study in the exact same population), and power of 90% (beta 0.1), this would require **63 clusters of 50 patients** in both arms, resulting in **6300 children**.

R code:

We used the n4props-function in the R package CRTSize, using the following command:

n4props(0.2065,0.1435,50,0.063, alpha = 0.05, power=0.9, AR=1, two.tailed=TRUE, digits=3)

Considering the pragmatic nature of this trial and in correspondence with the 10% of practices performing nonconsecutive inclusion of patients (high risk of selection bias) during the ERNIE2 trial, we will perform sensitivity analyses only considering physicians who have recruited in a consecutive way. Taking into account the required sample size for this analysis of the primary study outcome, these assumptions result in a total sample size of 7000 patients for the primary study outcome.

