- multicentre: six academic centres for primary care will be involved in the recruitment of 122 primary care practices
- pragmatic: criteria excluding patients from participation will be limited as well as procedures that do not reflect care as usual
- cluster: randomization occurs at the level of the primary care practice while patients are the unit of analysis
- randomized: block randomization per academic centre will be performed to assign primary care practices to either the intervention or the control arm
- controlled: the intervention will be compared with usual care
- superiority: the trial is designed to show that the intervention is superior to usual care

Randomization

In order to avoid contamination between physicians working in the same practice, randomization will happen at the level of the physician's practice.

General practice clinics and community paediatric centres will be randomized in one of the two study arms in a 1:1 ratio using a block randomization system stratified per recruiting academic centre in order to guarantee that allocation to either the usual care or the intervention arm is balanced within every region.

Stratified block randomization will be done using an electronic random numbers generator in blocks of four practices. Randomization and concealment will be centralized at the KU Leuven and conducted by a staff member not involved in data collection or delivering the intervention.

Sample size calculation

The original sample size calculation in the approved protocol version 2.0 was based on previous data from the ERNIE2 trial, assuming an overall antibiotic prescribing proportion of 26.5% in those children recruited for our trial.

The overall antibiotic proportion was found to be 18% in the first 4938 patients recruited in the ARON trial.

If we were to assume a reduction of 5.3% (proportionate to our original reduction) between the usual care group and the intervention group, using a 5% significance level (alpha 0.05), an intracluster correlation coefficient (ICC) of 0.063 (based on data from the ERNIE2 trial in the exact same population), and power of 90% (beta 0.1), this would require 63 clusters of 50 patients in both arms, resulting in 6300 children.

R code:

We used the n4props-function in the R package CRTSize, using the following command: n4props(pc = 0.2065, pe = 0.1435, m = 50, ICC = 0.063, alpha = 0.05, power=0.9, AR=1, two.tailed=TRUE, digits=3).

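### The revised sample size was computed for a 6.3-point reduction, not the stated 5.3 points, so power for the stated target is about 77%, not 90%

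*Protocol*

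**What the plan says.** Protocol section 11.1.2 (part 2, sample size) and the SAP section on sample size revise the target because antibiotic prescribing was lower than planned. The protocol reports: "The overall prevalence was found to be 18% overall in children recruited in the first 4938 patients recruited in the ARON trial". It then sets the new effect: "If we were to assume a reduction of 5.3% (proportionate to our original reduction) between the usual care group and the intervention group". The SAP says the same. The reference point is the initial calculation in section 11.1.1, where the target is given (in percent) as "from 30.43% to 22.65".

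The command printed in the protocol is "n4props(0.2065,0.1435,50,0.063, alpha = 0.05, power=0.9, AR=1, two.tailed=TRUE, digits=3". The SAP prints the same inputs: "n4props(pc = 0.2065, pe = 0.1435, m = 50, ICC = 0.063, alpha = 0.05, power=0.9, AR=1, two.tailed=TRUE, digits=3". Both documents draw the same result from it, in the SAP's words "this would require 63 clusters of 50 patients in both arms, resulting in 6300 children". Dividing by 0.9, to allow for practices that do not recruit consecutively, gives 7000.

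The number of practices is unchanged. The SAP design section says "six academic centres for primary care will be involved in the recruitment of 122 primary care practices", and protocol sections 5 and 6 also give 122.

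**The concern.** The text and the command describe different effects: 20.65 − 14.35 = 6.30 points, not 5.3. Required sample size varies with the inverse square of the difference, so a one-point slip at this size changes the answer by nearly half. If the text gives the intended target, the trial does not have its claimed 90% power. A non-significant result could then be taken as a 1-in-10 miss of a 5.3-point effect, when the chance of missing it is nearer 1 in 4 or 1 in 5.

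The revised calculation also implies 2 × 63 = 126 practices of 50 children, or 7000 / 50 = 140 after the allowance, yet both documents still plan 122.

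**Working it through.** **Inputs.** From protocol 11.1.1 and 11.1.2 and the SAP sample size section: two-sided alpha 0.05, power 0.90, ICC 0.063, m = 50 children per cluster, 1:1 allocation, N = 7000. From protocol sections 5 and 6 and the SAP design section: 122 practices, so 61 per arm.

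**Formula.** Clusters per arm:

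k = (z₀.₉₇₅ + z₀.₉₀)² × [p₁(1−p₁) + p₂(1−p₂)] × [1 + (m−1)·ICC] / [m (p₁−p₂)²]

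Here (1.960 + 1.2816)² = 10.51, and the design effect is 1 + 49 × 0.063 = 4.087.

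**Step 1: reproduce the plan's figures, then apply the stated target.**

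| Rates | Difference | k per arm | Children | After /0.9 |
|---|---|---|---|---|
| 30.43% vs 22.65% (initial) | 7.78 | 54.9 → 55 | 5500 | – |
| 20.65% vs 14.35% (revised command) | 6.3 | 62.05 → 63 | 6300 | 7000 |
| 20.65% vs 15.35% (revised text) | 5.3 | 89.8 → 90 | 9000 | 10,000 |

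The first two rows match the documents, so the formula is the right one and the stated totals follow from the command, not from the text.

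**Step 2: which rates does the text imply?**
- The initial rates average (30.43 + 22.65)/2 = 26.54%, the 26.5% overall rate that both documents quote.
- Scaling the initial reduction to 18% gives 18 × 7.78/26.54 = 5.28 points, the stated 5.3.
- The control rate in the command is 18% plus half of 5.3: 18 + 2.65 = 20.65%. The matching intervention rate is 18 − 2.65 = 15.35%.
- Relative reductions are 7.78/30.43 = 25.6% initially, 5.3/20.65 = 25.7% with 15.35%, and 6.3/20.65 = 30.5% with the printed 14.35%. The command's rates average 17.5%, not 18%.

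**Step 3: can another calculation turn 5.3 points into 63 clusters?** At two-sided 90% power, across unpooled, pooled, t-based and continuity-corrected versions, k is 89.8 to 93.2 for 20.65 vs 15.35. It is 85.9 to 89.2 for 19.65 vs 14.35, and 79.0 to 82.4 for 18.0 vs 12.7. None gives 63.

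**Step 4: power for 20.65% vs 15.35%.** Power = Φ(0.053/SE − 1.96), where SE² = [0.2065 × 0.7935 + 0.1535 × 0.8465] × DE / n = 0.2938 × DE / n, and n is children per arm.
- 7000 in 122 practices: m = 57.4, DE = 1 + 56.4 × 0.063 = 4.55, n = 3500, SE = 0.01955, power = Φ(0.751) = 77.4% (76.7% with a t reference).
- 63 × 50 per arm: 77.5%.
- 70 × 50 per arm (140 practices): 81.6%.
- Consecutive recruiters only, if 10% of practices and 10% of children are lost (about 6300 children in 110 practices): about 73%.
- Ceiling with 61 practices per arm: as m grows, DE/m tends to 0.063, so SE tends to √(0.2938 × 0.063/61) = 0.01742 and power to about 86%.

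For 20.65% vs 14.35%, 7000 children in 122 practices give 90.4% power.

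**The case against.** The documents never print 15.35% and never call 14.35% a slip. The command, 63 clusters, 6300 and 7000 agree with one another, so the 5.3 in the text could be the error. That is possible, but the text then fails twice: 6.3 points is not in proportion to the initial reduction, and the command's rates do not average 18%. On either reading a correction is needed.

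The 77% also depends on where the 5.3 points are placed and on the number of practices. With 7000 in 122 practices, 19.65% vs 14.35% gives 79.2% and 18.0% vs 12.7% gives 82.4%. With 70 × 50 per arm the highest of these rises to 86.2%. This stands as a qualification, but every combination is below 90%.

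The figure of 122 looks like a carry-over from the initial total (6111/50 = 122.2), and protocol section 11.2 applies it to physicians. It is a planning number, and the number of practices that actually recruited is not given. The 86% ceiling rests on it too. The 73% assumes that 10% of practices take 10% of the children with them. Low recruiters would take fewer, and protocol section 11.3.4 puts the excluded share at about 5% of practices where the SAP says 10%, so the true figure probably lies between 73% and 77%.

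Finally, the slip does not touch the analysis model, the estimate, its confidence interval or the type I error rate. That is correct. What is wrong is the power claim.

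**Conclusion.** The concern holds. Both documents claim 90% power for a 5.3-point reduction, but the calculation behind the claim used 6.3 points. For 20.65% versus 15.35%, 7000 children give about 77% power in 122 practices and about 82% in 140 practices of 50. Ninety per cent power would need 90 clusters of 50 per arm.

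These figures assume ICC 0.063, a two-sided 5% test, equal cluster sizes and a reduction centred on 18%. Unequal cluster sizes would lower power further. Other placements of 5.3 points raise it somewhat, but to no more than 86.2%. With 61 practices per arm, more children per practice cannot close the gap for 20.65% versus 15.35%, because power cannot pass about 86%.

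**What to change.** Amend protocol section 11.1.2 and the SAP sample size section in one of two ways:

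1. Keep 5.3 points, enter 0.2065 and 0.1535 in the command, and state that 7000 children in 122 practices give about 77% power.
2. Keep the command, state that 90% power refers to 20.65% versus 14.35% (6.3 points, 30.5% relative), and delete the 5.3% figure and the claim that it is proportionate to the initial reduction.

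In either case, compute power for the actual number of practices and children per practice (about 57 each if 122 is right), and bring the 122 in protocol sections 5, 6 and 11.2 and in the SAP into line with the revised calculation. State how many practices and children are assumed lost in any power figure for the consecutive-recruiter analysis.

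The cost is wording in two documents and a less favourable power statement or a larger stated target. No patients are added and the analysis does not change.

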11.2 Planned recruitment rate

Our groups have successfully completed a range of trials in both children and adults with acute illnesses in primary care.

The same primary care network used in previous studies by the sponsors group will be used for recruitment, previously resulting in sample sizes of up to 8962 children.

The planned recruitment period will be 21 months. Taking into account an inclusion rate of 1 in 5 of all eligible children, we will include a total of 122 ambulatory care physicians.

11.3 Statistical analysis plan

11.3.1 Summary of baseline data and flow of patients

Presentation of baseline characteristics of the study population and comparability of the 2 arms will be based on the following variables:

- Age (median and 25-75 percentiles)
- Gender (percentage)
- Ethnicity (percentages)
- Parental smoking status (percentage)

Differences in baseline characteristics and clinical features will be analysed through Chi-squared testing and nonparametric equality-of-medians testing to assess potential recruitment bias.

11.3.2 Primary outcome analysis

The primary endpoint will be analyzed according to the intent-to-treat (ITT) approach.

We will use a mixed-effects logistic regression analysis to account for the clustering at practice level, and other potential interaction terms, such as the child's age.

Multiple imputation will be applied to deal with missing data. Imputation will be performed for the binary outcome variable and logistic regression will be used as imputation model. Predictors for the imputation model are baseline patient characteristics and intervention.

Subgroup analysis will be performed in order to investigate how the primary outcome behaves in function of:

- age categories
- gender

11.3.3 Secondary outcome analysis

We will use a mixed-effects logistic regression analysis to account for the clustering at practice level, and other potential interaction terms, such as the child's age.

Multiple imputation will be applied to deal with missing data. Imputation will be performed for the binary outcome variable and logistic regression will be used as imputation model. Predictors for the imputation model are baseline patient characteristics and intervention.

11.3.4 Procedure(s) to account for missing or spurious data

Drop-outs are unlikely to be a large problem since there will be only 1 study visit complemented by the collection of follow-up information.

We will analyze the whole population for the primary analysis and perform a sensitivity analysis excluding the low recruiting practices (less than 10 patients recruited during 12 months) to avoid our results to be susceptible to selection bias. In previous trials this resulted in approximately 5% of practices who did not contribute to these sensitivity analyses as the risk of selection bias was deemed extremely high in these practices.

Practices that do not recruit children at all will be stopped after the first two monitoring visits and replaced by new practices to avoid reducing the total number of clusters, available for analysis.

See section 8.6 for strategies to maximize follow-up and to prevent missing data. See sections 11.3.2 and 11.3.3 for statistical handling of missing data.

The percentage of missing data for the primary outcome measure of antibiotic prescribing rate is expected to be low as this will be registered at the first-contact consultation. In our previous trial, we found 4% of missing data for the primary outcome of antibiotic prescribing rate. Multiple imputation will be considered for the primary outcome measure as well as missing values for patient-reported outcomes (if there are any). Other outcomes will be collected in the patient health record of the physician.

11.4 Data collection for economic evaluation

One of the goals of the KCE Trials programme is to improve the efficiency of the healthcare system. This protocol has been designed with a later possible economic analysis in mind. The planned economic analysis is briefly described below, together with the variables collected in this protocol for this purpose. For the sake of clarity, the economic analysis is not a part of this trial. The decision to conduct such economic analysis will depend on the effectiveness results of this trial.

OVERVIEW

The first part is a cost study with the aim to identify significant cost drivers and to compare the cost impact of the intervention with its alternative 'usual care'. A cost driver is a component in the health service significantly associated with the costs. The potential subcategories of costs considered are: acute outpatient, acute inpatient, primary care, residential care, pharmacy prescriptions, chronic prescriptions, diagnostic tests, visit to A&E, intervention costs.(30) A health care payer perspective is adopted and includes payments out of the federal government's and the communities' health care budget as well as patients' co-payments.

The second part on the economic evaluation concerns cost-consequences analysis, comparing costs and consequences (expressed in hospitalizations, consultations, pharmaceuticals (re-imbursed and non-reimbursed) and productivity) and cost-utility-analysis (CUA) using broader metrics such as QALYs, between participants in the 'intervention' study group (intervention group) and those in the 'usual care' study group (control group). The goal of this analysis is to indicate the technical and allocative efficiency (cost per effect) of the intervention and care as usual.

ANALYSES

Part I: cost estimations

In both study groups (with about N=3056 in every group), the subcategory costs (pharmaceuticals, consultation, hospitalization, productivity) and total costs per patient will be calculated. These costs include : the direct medical costs of healthcare use for which a nomenclature code exist and which will be tracable in the datasets that we will have access to (see also below) and the cost of the intervention itself (the POC testing), and: the indirect costs for patients (e.g. caregiver time, cost of absenteeism and presenteeism, administrative costs). In addition, between-group differences are calculated for each subcategory and total costs. First, descriptive statistics will provide

unadjusted information on the magnitude and distribution of the 'intervention' costs for each of the subcategories compared to the 'usual care' group. Secondly, generalized linear modelling (GLM) will be applied to evaluate the total costs between both groups adjusted for the other independent factors (patient characteristics, cluster, etc).

Part II: health economic evaluation (CUA) Bottom-up approach:

In this phase, an analysis of the costs and health effects alongside the clinical trial will be conducted. The effects will be expressed broadly as consequences (e.g. hospitalizations or cases avoided) but also as 'utilities' (i.e. a health-related quality of life weight, range from 0 [dead] to 1 [perfect health], i.e. QALYs).

For both study groups, resource use data and health-related quality of life (HRQOL) data will be collected during the trial using information from the patients' health records and using a questionnaire (self-reported) as part of the smartphone app for parents for those resources not captured by the health records. Simultaneously, information from the RIZIV nomenclature database will be used to attach costs to the different resource use data. Alongside the data collected from the app during the trial, the costs associated with hospitalisation, consultations, pharmaceuticals (re-imbursed) during follow-up will be collected by linking the national insurance number (collected during the index consultation by the participating physician) of children via a trusted third party to the administrative databases reporting on healthcare usage. The HRQOL data will be collected using the proxy version of the EQ-5D-Y questionnaire (24) (filled out at regular timings by the participants (by parents). As we anticipate a large proportion of our study population to be below the age of 4 years, we will include additional scales aiming to assess quality of life or rather pain as this is assumed to be the main driver for quality of life in the young infants and has shown to have face validity:

- The Wong Baker FACES Pain Scale (25), which has been validated in children from 3 years to 18 years of age (31)
- The FLACC scale (26), which has been validated in children from 0 to 18 years of age (32)

Resource use data will be collected during follow-up by linking the national insurance number to the administrative healthcare usage databases, as well as from the data collected in the parental app (hospitalization, consultation). This complementary approach is preferred to avoid missing data and assess representativeness of our analysis.

Health-related quality of life data will be collected at regular time points: at day 1, day 4, and day 7 for all children and each week thereafter for children that have not recovered after day 7 (maximum up to day 28).

Information related to the intervention costs will be collected in the nested qualitative study, including the physician's time spent on the program (as reported by the participating physicians in the nested qualitative substudy). The latter costs will be recalculated at patient level.

The ratio of the incremental costs to the incremental effects is called the incremental cost-effectiveness ratio (ICER) calculated as: $(Cost_N - Cost_C)/(Health effect_N - Health effect_C)a$. This measure reflects the difference in costs per unit of effect. We will calculate ICERs in terms of natural effects (number of packages AB prescribed) and in terms of QALYs, or net benefits (in case of dominated or dominant interventions).

A well-known issue is the presence of missing data related to the different outcome variables (cost data). Different methods exist to handle this. In the current research project, single imputation methods will be used. In this method, the missing data are replaced with a single predicted value (e.g. the adjusted mean value).(33) Sensitivity analyses will be conducted to determine how different input values will impact the outcome.(33)

Decision-analytic model will be used to predict longer-term patient outcomes and complications for patients as well as their economic impact in the 'intervention' arm versus the 'usual care' arm, as well as to investigate the effect of changes in particular parameters (sensitivity analysis). We will use a combination of decision-trees and markov models to follow hypothetical cohorts over time. The main data as input for the model will be the occurrence of hospital admission for serious infection, health outcomes for non-hospitalized patients and reported cost and HRQoL data (obtained from phase 1 and in case needed from published literature). This kind of model allows us to simulate transitions in various health states beyond the duration of the intervention, and as each health state is associated with costs and utilities, to estimate cost-effectiveness ratios. The health effects in this model will be mainly expressed as quality-adjusted life years (QALYs). QALYs are calculated by multiplying the utility level (information obtained in phase 1) with the number of years and individual lives with the condition.

Health economic evaluation studies are frequently characterized by degrees of uncertainty or methodological considerations. In the current study, one-way, multi-way and probabilistic (monte carlo/non-parametric bootstrapping) sensitivity analyses will be conducted to handle various uncertainties. Uncertainty analyses will be expressed in terms of cost-effectiveness acceptability curves.

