 - Calculation of costs: In both study groups, the subcategory costs and total costs per patient will be calculated. These costs include the direct medical costs of healthcare use, the cost of the intervention itself, and the indirect costs for patients.
 - Between-group differences: Differences between the intervention and control groups will be calculated for each subcategory and total costs.
 - Descriptive Statistics: Initial assessment of cost difference will involve descriptive statistics to provide unadjusted information regarding the magnitude and distribution of the costs. T-tests and Mann-Whitney U tests will be employed to assess differences between the randomization groups.
 - Generalized Linear Modelling: To evaluate total cost differences between both groups while adjusting for independent factors such as patient characteristics (age and gender).
- Cost-consequences analysis:
 - Compares costs and consequences, encompassing hospitalizations, consultations, pharmaceuticals, and productivity between intervention and control group.
 - Considers perspectives from healthcare payers and society.
 - Utilizes decision-analytic modelling, employing a combination of decision trees and Markov models to track hypothetical cohorts over time.
 - The results of this analysis will be presented as incremental cost-effectiveness ratios, calculated based on natural effects. In case of a dominant or dominated intervention, net benefits will be computed and plotted on a net benefit plot.
- Cost-utility analysis:
 - Compares costs and 'utilities' (calculated using HRQoL data collected through questionnaires in ARON app and the Belgian value set for the EQ5D-Y questionnaire) between intervention and control group.
 - Considers perspectives from healthcare payers and society.
 - Utilizes decision-analytic modelling, employing a combination of decision trees and Markov models to track hypothetical cohorts over time.
 - The results of this analysis will be presented as incremental cost-utility ratios, calculated based on Quality-Adjusted Life Years (QALYs). In case of a dominant or dominated intervention, net benefits will be computed and plotted on a net benefit plot.

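### The protocol's cost study takes a health care payer perspective, but its only adjusted comparison is run on a total that includes productivity and other indirect costs, and the SAP does not assign cost items to its two perspectives

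*Protocol*

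**What the plan says.** Protocol section 11.4 describes the economic work in two parts, the first being a cost study. In the Overview paragraph on that first part, the perspective is fixed: "A health care payer perspective is adopted and includes payments out of the federal" government's and the communities' health budgets, together with co-payments by patients. The potential cost subcategories listed there are "acute outpatient, acute inpatient, primary care, residential care, pharmacy prescriptions, chronic prescriptions, diagnostic tests, visit to A&E, intervention costs". All are health-service items or the intervention itself.

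Under Part I (cost estimations) of the same section, the list changes: "the subcategory costs (pharmaceuticals, consultation, hospitalization, productivity) and total costs per patient will be calculated". The costs counted are direct medical costs, the cost of the point-of-care testing, and "the indirect costs for patients (e.g. caregiver time, cost of absenteeism and presenteeism, administrative costs". For reporting, "between-group differences are calculated for each subcategory and total costs"; for the adjusted analysis, "generalized linear modelling (GLM) will be applied to evaluate the total costs between both groups".

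The SAP costing study says: "These costs include the direct medical costs of healthcare use, the cost of the intervention itself, and the indirect costs for patients". It also calculates differences for each subcategory and for the total, and fits a generalized linear model to total cost. It names no perspective for this study. For the cost-consequences analysis, and again for the cost-utility analysis, it says: "Considers perspectives from healthcare payers and society". It does not list the cost items that belong to each perspective.

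**The concern.** The perspective decides which costs count. Caregiver time and lost work are not paid from public health budgets and are not co-payments, so a total that contains them is not a payer cost. The protocol announces one quantity and specifies the adjusted analysis of another.

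The SAP does not settle the matter. It keeps a single total with indirect costs, then adds a second perspective elsewhere without saying what goes into the numerator of each ratio. An analyst would have to decide that while writing the report, possibly after seeing which definition gives the more favourable answer. At stake is whether the cost result given to the funder means what section 11.4 says it means. That section opens by naming health-system efficiency as a goal of the funding programme.

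**Working it through.** The check is mainly a comparison of passages, because the point concerns which costs are counted.

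**The one figure in the section.** Part I gives about 3056 patients per group. It follows from the initial sample size: 5500 / 0.9 = 6111, and 6111 / 2 = 3055.5. The current target of 7000 gives 7000 / 2 = 3500 per group, so 3056 is out of date. Nothing below depends on it.

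**Passages side by side.**

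| Place | Perspective stated | Indirect costs counted? | Adjusted comparison |
|---|---|---|---|
| Protocol 11.4, Overview (cost study) | Health care payer | None in the list of subcategories | – |
| Protocol 11.4, Part I (same study) | None restated | Yes: productivity, caregiver time, absenteeism, presenteeism, administrative costs | One model, on total costs |
| SAP, costing study | None | Yes: indirect costs for patients, not itemised | One model, on total cost |
| SAP, cost-consequences and cost-utility analyses | Payer and society | Not stated by perspective | – |

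The first two rows concern the same study and disagree. The last two leave the assignment of items to perspectives open.

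**What the single total estimates.** For each child, total cost = payer cost + indirect cost. Taking mean differences between arms:

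total-cost difference = payer-cost difference + indirect-cost difference.

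The total gives the payer answer only if the indirect-cost difference is zero.

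**Illustration, with assumed values** (the documents give none; any currency unit). Let the payer-cost difference be +5 per child.

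| Indirect-cost difference | Total-cost difference |
|---|---|
| −10 | 5 − 10 = −5 |
| −5 | 5 − 5 = 0 |
| 0 | 5 + 0 = +5 |
| +5 | 5 + 5 = +10 |

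So the total can agree with the payer answer, overstate it, hide it or reverse its sign. Which of these would happen in this trial cannot be computed from the documents.

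**What can be recovered.** Unadjusted mean differences add up. Because both documents report differences by subcategory, and Part I makes productivity its own subcategory, an unadjusted payer difference can be obtained by leaving out the indirect items. No adjusted comparison is planned for any subcategory, so an adjusted payer difference cannot be obtained in this way.

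**The case against.** The strongest reply is that little is lost. The total is a sensible quantity in its own right, being close to a societal cost. Subcategory differences are reported, so a reader can remove productivity. The SAP attaches its two perspectives to the cost-consequences and cost-utility analyses, not to the costing study, and nowhere says that both will use the same total. Cost-effectiveness is one of many exploratory endpoints, and section 11.4 places the economic analysis outside the trial and makes it depend on the effectiveness results.

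Most of this stands and limits the point. It does not remove the contradiction within section 11.4, it does not supply an adjusted payer comparison, and the SAP's silence on cost items is itself the gap. The SAP also schedules the economic study for January to February 2025, so it is more than a remote possibility.

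A reader might infer four stronger things that the documents do not support:

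- *That the cost comparison answers no question at all.* It comes close to answering the societal one. What it fails to answer is the stated payer question.
- *That productivity is counted twice in the ratios, because it is listed both as a cost and as a consequence.* Section 11.4 names the effects used in the ratios as antibiotic packages prescribed and QALYs, and no planned ratio has productivity as its effect. Hospitalizations and consultations also appear on both sides; listing consequences beside costs is not adding them together.
- *That indirect costs would swamp the precision of the comparison through drop-out from the parent app.* The descriptions of app content in Protocol section 8.7 and in the SAP's Data Source section do not list caregiver time or absenteeism, so the app cannot be taken as their stated source. Any figure for precision rests on assumed standard deviations. With an assumed correlation of 0.3, the ratio of standard errors, √(SDd² + SDi² + 0.6·SDd·SDi)/SDd for direct (d) and indirect (i) costs, is 6.37 at 50 and 300 but 1.05 at 150 and 20. It also compares two different quantities, so it does not measure error in either.
- *That the protocol makes the payer view the base case for the whole economic evaluation.* It does not use that term, and the payer sentence belongs to the paragraph on the cost study.

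**Conclusion.** The point holds in a limited form. Section 11.4 adopts a payer perspective for the cost study and then specifies its only adjusted comparison on a total that includes costs no payer bears. The SAP repeats the mixed total and does not say which costs enter its payer and societal analyses. Followed as written, the adjusted result is close to a societal cost difference and would not be the payer difference announced.

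The gap equals the indirect-cost difference between arms, and its size is unknown. The conclusion rests on two readings: that Part I elaborates the cost study named in the Overview, and that caregiver time and lost work lie outside public health budgets and co-payments. Both follow from the text. The effect is confined to an exploratory, conditional analysis; no primary or secondary conclusion depends on it. It should be corrected before the economic analysis is run.

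**What to change.** In Protocol section 11.4 and in the SAP costing study:

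1. Define a **payer total**: direct medical costs, the cost of the intervention, and co-payments.
2. Define a **societal total**: the payer total plus the indirect costs, with the items listed (caregiver time, absenteeism, presenteeism, administrative costs).
3. Run the between-group comparison and the generalized linear model on each total. Use the payer total for the cost study, in line with the perspective already stated in the Overview.
4. For the cost-consequences and cost-utility analyses, state which total is used under the payer perspective and which under the societal one.

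The cost is a change of wording in both documents and one further run of the same model. The split needs no cost items beyond those that Part I already sets out to count. The downside is two sets of cost results to report and explain instead of one.
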